## **5.7 Withdrawal of Subjects**

- Describe any anticipated circumstances under which subjects will be withdrawn from the research without their consent.
- Describe the consequences of a subject's decision to withdraw from the research and the procedures for orderly termination of participation by the subject (e.g., the subject contacting the investigator for an end-of-study visit).

We do not anticipate any circumstances under which subjects will be withdrawn from the research without their consent. In our previous peer support trials, this has not occurred. The only circumstance where a participant would be withdrawn from the study would be in the event of threatening or unsafe behavior toward the study staff or peer health coaches. If a participant decides to stop the study for any reason, the intervention visits would end and study personnel would attempt to schedule an exit visit.

## 7.0 Privacy and Confidentiality

- Describe whether the study will use or disclose subjects' Protected Health Information (PHI).
- Describe the steps that will be taken to secure the data (e.g., training, authorization of access, password protection, encryption, physical controls, Certificates of Confidentiality, and separation of identifiers and data)

Several steps will be taken to minimize the risk of invasion of privacy. Initial contact with prospective participants will be made via an introductory letter with a stamped post card allowing her/him to opt out of further contact by the study team thus limiting risk for invasion of privacy. A number of steps will be taken to ensure confidentiality and data protection throughout the rest of the study. All data gathered at the enrollment visit (the questionnaire, physical exam, health goals) and subsequent information will be confidential. Data will be kept in offices at VA Puget Sound HSR&D with locked filing cabinets and password protected computers. The investigators, project coordinator, and study staff will be the only staff to have access to confidential records. ID numbers rather than names will be used whenever possible. As part of the study, individuals will be reassured that information is to be kept confidential, no single individual will be identified by name and all data will be aggregated. All data files will be maintained on password protected PCs and password protected computer networks. Only aggregate data will be presented to external audiences. Individual identifiers will be deleted when they are no longer necessary for the project.

## 8.0 Communication Plan

- Include a plan for obtaining required coordinating site approval (if we are a participating site of a multi-site study).
- Include plan for keeping all engaged sites informed of changes to the protocol, informed consent, and HIPAA authorization, if we are the coordinating center. If we are a participating site, include a plan for how this information will be shared with you by the coordinating center.
- Include plan for informing local sites of any Serious Adverse Events, Unanticipated Problems, or interim results that may impact conduct of the study if we are the coordinating center. If we are a participating site, include a plan for how this information will be shared with you by the coordinating center.

**N/A – We have 1 primary site.**

## 9.0 Information Security and Privacy

The principal investigator will review critical incidents (participant death and hospitalization). For each such event, [name] will evaluate the potential for causal relations between the incident and study or intervention procedures. Any adverse effects of the study will be reported to the participant and his/her health care provider. Major adverse events requiring hospitalization will be reported to

the study project manager and the IRB. [name] will be available to meet with the participant and provider to discuss any concerns. The participants will bear no financial risk from any adverse effects of encounters from this study. Including only numeric identifiers on all data collection instruments will protect confidentiality of collected information. Code keys and data collection documents (when not in use) will be kept in a locked file or password-protected terminals.

Several steps will be taken to minimize the risk of invasion of privacy. Initial contact with prospective participants will be made via an introductory letter with a stamped post card allowing her/him to opt out of further contact by the study team thus limiting risk for invasion of privacy. A number of steps will be taken to ensure confidentiality and data protection throughout the rest of the study. All data gathered at the enrollment visit (the questionnaire, physical exam, health goals) and subsequent information will be confidential. Data will be kept in offices at VA Puget Sound HSR&D with locked filing cabinets and password protected computers. The investigators, project coordinator, and study staff will be the only staff to have access to confidential records. ID numbers rather than names will be used whenever possible. As part of the study, individuals will be reassured that information is to be kept confidential, no single individual will be identified by name and all data will be aggregated. All data files will be maintained on password protected PCs and password protected computer networks. Only aggregate data will be presented to external audiences. Individual identifiers will be deleted when they are no longer necessary for the project.

1. STUDY SUMMARY AND AIMS

A. Study purpose:

The overall goal of this study is to test the effectiveness of a home-visit peer health coach intervention (**Vet-COACH “Veteran peer Coaches Optimizing and Advancing Cardiac Health”**) to promote health behavior change among Veterans with multiple CVD risk factors with a hybrid type 1 implementation study.

B. Study design:

Randomized controlled trial to evaluate the effectiveness of Vet-COACH, a peer health coach home visit program to control hypertension and reduce CVD risk among Veterans.

Randomization

Following baseline assessments, a computerized randomization procedure assigned individuals to either the peer health coach intervention or to the usual care + education control group. Randomization occurred in the order of completed enrollment visits. Randomization lists were constructed using variable length blocks to ensure the groups were not unbalanced at any time. Concealment was used to prevent the study staff from obtaining information on the sequence of assignment.

C. Specific aims:

1. Test the effectiveness of a peer health coach intervention for improving health outcomes for Veterans with multiple CVD risks in a randomized controlled trial.
 - a. The **primary outcome** is a reduction in systolic blood pressure (SBP) from baseline to follow-up at 1 year.
 - b. **Secondary outcomes** include change in cardiovascular risk, as measured by the Framingham Risk Score, other cardiovascular risks (tobacco use, lipids) and health related quality of life. Using administrative data at 1 year following randomization, we will examine healthcare utilization, hospitalizations, and emergency room visits.
2. Assess the effects of a peer health coach intervention on intermediate outcomes that are intervention targets including social support, patient activation, patient/provider communication and health behaviors (e.g. medication adherence, physical activity, nutrition, alcohol use, and stress management).
3. Assess the cost of the intervention to inform feasibility for future studies.
4. Determine Veteran and staff satisfaction with the intervention and identify barriers and facilitators to adoption. [qualitative study not covered in this analysis plan]

3. STUDY POPULATION

Age up to 70 years; Poorly controlled hypertension (> 150/90 mmHg) in the year prior to enrollment and at least one other CVD risk (overweight or obesity, body mass index (BMI) \geq 25 kg/m², tobacco use, hyperlipidemia LDL-c > 130 mg/dL)

Exclusion criteria

Hospitalized in the past 3 months for CV related conditions (IHD, CVA, PVD)
Severe illness that precludes lifestyle program, ESRD on dialysis
Nursing home resident, homeless
Severe cognitive impairment
Receiving home-based primary care or home telehealth services
Presence of suicide and/or behavioral risk flag in CPRS

4. STUDY TIME PERIOD

Enrollment period: 2017 - 2021

5. STUDY OUTCOMES

Primary outcome:

Primary outcome -- continuous change in systolic blood pressure. At baseline and exit (12 months); 3 blood pressure readings were obtained using standard procedures. The average of the 3 blood pressure measurements is used. Blood pressure was assessed at a baseline enrollment visit using standardized protocols, measured by a trained research assistant, using an A&D Medical Ua-767f Multi-User Blood Pressure Monitor blood pressure cuff. Measurements were taken three times. If participant failed to schedule an exit visit, blood pressures were extracted from the medical record for a 3-month period around the date of the exit visit. The lowest value will be used from the CDW for that day.

Secondary outcomes:

Secondary outcome — SBP control. This is a dichotomous outcome in which control is defined as the percentage of respondents meeting pre-specified blood pressure goal (BP \leq 120/80) as based on current VHA/DOD/AHA guidelines.

BP Category	SBP		DBP
Normal	<120 mm Hg	and	<80 mm Hg
Elevated	120–129 mm Hg	and	<80 mm Hg
Hypertension			
Stage 1	130–139 mm Hg	or	80–89 mm Hg
Stage 2	\geq 140 mm Hg	or	\geq 90 mm Hg

All outcomes were measured at baseline and at 12 months. Laboratory examination at both baseline and follow-up includes a non-fasting lipid panel (total, low density lipoprotein [LDL] and high-density lipoprotein [HDL] cholesterol; triglycerides) and are utilized to calculate one of the secondary outcomes, the Framingham Risk Score. Other secondary outcomes include health-related quality of life (HRQOL) measured with the SF-12 and health care utilization.

Intermediate outcomes:

Self-management behaviors were measured at baseline and 12-months that are intermediate outcomes, such as nutrition, physical activity and medication adherence. The nutritional assessment includes a self-reported assessment of dietary intake “Starting the conversation” an eight-item validated, simplified food frequency instrument designed for use in primary care and health-promotion settings. Level of physical activity at baseline and follow-up is assessed using the International Physical Activity Questionnaire (IPAQ), a validated and reliable measure of physical activity (PA) level that classifies participants as high (e.g. over 60 minutes of moderate-intensity PA per day), moderate (e.g. 30 minutes of at least moderate-intensity PA on most days), or low. Medication adherence is assessed using a standardized participant interview.

Covariates:

Key covariates include those that have been shown in previous studies to be associated with hypertension control and self-care. Self-reported demographic covariates include age, gender, marital status, education, annual income and race/ethnicity. Self-reported race and ethnicity questions were taken from the Behavioral Risk Factor Surveillance System (BRFSS) Questionnaire. Race responses were then classified as American Indian or Alaskan Native, Asian Indian, Chinese, Filipino, Japanese, Korean, Vietnamese, Native Hawaiian, Guamanian or Chamorro, Samoan, Black or African-American, White or other. We ask them separately to define their ethnicity as Hispanic, Latino or Spanish origin. We include questions to measure health literacy in adults. We assess alcohol consumption using the Alcohol Use Disorders Identification Test (AUDIT-C), a 3-item screening test for heavy drinking and/or abuse. Because of the strong link between depression and poor self-care, depressive symptoms are assessed using the Patient Health Questionnaire-8 (PHQ-8). We also collect data on costs and utilization obtained from VHA administrative data.

Outcome Measures; measured at baseline and 12 months		
	Measurement domain	Measurement instrument
Primary outcome		
Blood pressure	Systolic blood pressure (SBP)	Standard protocols
Secondary outcomes		
Cardiovascular risk	Framingham risk score (FRS)	FRS algorithms
Individual Cardio-metabolic risks	Body Mass Index (BMI)	Standard protocols for height and weight
	Low density lipoprotein cholesterol (LDL-c)	Laboratory data from CPRS if within 12 months of enrollment, otherwise drawn at enrollment, and within 3 months of the exit visit
	Tobacco use	Self-report from BRFSS questions
Health Care Utilization	Outpatient (including specialty care visits) and ER visits, hospitalizations utilization.	Self-report and VA administrative data
Health-related quality of life	Role limitations caused by physical health, emotional problems, physical functioning, and general health	SF-12

Outcome Measures; measured at baseline and 12 months		
Intermediate outcomes		
Patient activation, Self-efficacy	Self-rated ability to take preventive actions, manage symptoms of medical problems, find and use appropriate medical care, and work with their health care providers	Consumer Health Activation Index (CHAI)
Social Support	Domains of Social support	8-item Medical Outcomes Study (MOS) Social Support Survey Instrument & Behavioral Risk Factor Surveillance System (BRFSS) Questionnaire
Self-management Behaviors – Measure of behavioral enactment	Physical activity Nutrition – eating behavior, food frequency Medication adherence Alcohol use Stress Management	IPAQ “Starting the conversation,” FFQ Voils et al Medication BRFSS AUDIT-C
Patient provider communication	Communication with physician and health care team	Consumer assessment of health plans (CAHPS)-patient provider communication

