**Enrollment and randomization:**

**a) Enrollment and exit visits**

The research coordinators will interview participants during the enrollment and exit visits over the phone. If a participant expresses completion of the exit survey over the phone would pose difficulties for them, staff will provide the option to complete and return the exit survey by mail. If the participant agrees, staff will mail a copy of the exit survey with a postage-paid return envelope to mail the completed survey to the HSR&D office. Study staff in possession of a VA-issued flip phone will use it to conduct the call. Study staff who do not have a VA phone or laptop will use their personal smart phone and conduct the call using the Doximity app. Scheduled participants will be mailed a letter prior to their enrollment visit that will confirm the date, time, and location of their appointment and a brief summary of what will be covered in the visit and program. The baseline enrollment visit and exit call will include blood pressure measurements and labs (lipids). If there are no lipid panel results in CPRS dated within 12 months prior to the baseline/enrollment date or 3 months prior to the exit visit date, the PI will order a lipid panel test. If a participant moves out of the Puget Sound area and/or receives lipid test results from a non-VA provider or clinic, we will request they send the lipid panel test results from the non-VA lab or VA lab in another state to the Puget Sound VA Primary Care Clinic via mail or secure fax. This is already done by VA patients who may get bloodwork at a non-VA facility. These results would be used as the lipid measurements typically collected at the exit visit. [name] (study coordinator and phlebotomist) will conduct the blood draw with participants completing the enrollment and/or exit visit with her. [name] has completed all the required trainings and coursework to conduct blood draws at the VA Puget Sound. Any results flagged as high will be reported by the PI to the participant's PCP -- either as an addendum to the research enrollment note or as an alert to the PCP if they are not enrolled in the study -- using the following statement: "We ordered a lipid panel test as part of screening or follow up for the Vet-Coach research project. Your patient may or may not participate in this study." Three blood pressure measurements will be collected by the research coordinators at intervals during the enrollment call. For BP measurement, after the patient has sat comfortably for 5 minutes, three BP consecutive measures are obtained and then averaged per NHANES protocol. All BP measurements will be performed with electronic, upper arm cuffs. The average BP must be  $>150/90$  mm Hg at the time of the data pull for Veterans to be eligible for the study. We will attempt to schedule enrollment visits within a week of their most recent primary care visit to recruit Veterans with uncontrolled hypertension. Height and weight will be measured at baseline and weight will be measured at exit. Measures collected include: chronic disease self-management behaviors, health history, health care access, and health care utilization. Urgent issues will be referred immediately to the PI. The PI will contact the PCP for urgent issues to ensure appropriate follow-up.

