### **Primary and secondary outcomes**

The primary outcome measures will be systolic blood pressure. At the baseline visit and the final 12 month exit call, the study staff will ask the participant to measure blood pressure three times. At the time of scheduling, study staff will ask if the participant has a blood pressure monitor and/or scale in their possession. If the participant does not have a monitor or scale, staff will mail them one from the VA office. The mean value for these readings will be used for the baseline and exit measurements, respectively.

Secondary outcomes will include Framingham Risk Score (FRS), individual CVD risks (BMI, LDL-c, tobacco use), health care utilization and health-related quality of life. A 10-year risk of total CVD (including myocardial infarction, angina, coronary revascularization, stroke, congestive heart failure and peripheral arterial disease) will be determined according to FRS algorithms, which include age, total and high-density lipoprotein-cholesterol, systolic blood pressure, treatment for hypertension, diabetes, and cigarette smoking. Individual components of this risk score are targets of the intervention (hypertension, hyperlipidemia, and smoking). The FRS algorithm has good predictive validity for CHD events (c statistics 0.74 and 0.77 for men

and women, respectively). Health care utilization will include outpatient visits, emergency department visits, and hospitalizations. Health care utilization will be obtained from VA administrative data and by participant self-report to capture non-VA health care utilization. Health-related quality of life will be measured by the Medical Outcomes Study 12-item measure, the SF-12. Two composite scales will be used to measure physical health (the physical component summary) and mental health (mental health component summary).

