All Aim 1 secondary outcomes and Aim 2 intermediate outcomes will be compared between intervention and control participants using the same model above for continuous outcomes and using a logit link for the same model for binary outcomes.

Sensitivity analyses

We will include a sensitivity analysis that will explore whether intervention fidelity influences the effect of the intervention on primary outcomes, treatment receipt (“dose” of intervention: number of visits, phone calls, proportion of required modules delivered). This approach will allow for testing whether greater participation in the intervention was associated with a greater impact on SBP, and if that impact was different for those with different SBP at baseline (include baseline blood pressure in the primary analysis). We will also add a sensitivity analysis among patients enrolled after the COVID pandemic, when all study activities were moved to remote/virtual.

Exploratory Analysis:

1. Restrict sample was restricted to patients who met criteria for uncontrolled hypertension (BP \geq 140/90 mmHg)
2. Pre- vs. During pandemic
 - a. Demographics of Veterans enrolled post-COVID versus pre-COVID – are the Veterans enrolled post-COVID different than Veterans enrolled pre-COVID?
 - b. Separate analysis of primary/secondary outcomes for (1) Veterans with 12 month outcome collected pre-COVID and (2) Veterans with 12 month outcome collected post-COVID – are treatment effects different post-COVID?
3. Secondary analyses to adjust for important baseline covariates in our models. Prespecified variables age, race [others to consider diabetes status because there is a different goal blood pressure for patients with diabetes]

Missing data analyses

If outcome is missing (e.g. exit blood pressure) then will use value in CPRS on the date closest to the exit date (must be +/- 3 months around the date of the exit visit).

- Use outpatient blood pressure as defined by EPRP (EPRP documentation in Teams)

For key analysis variables that have 15% or more missing values, we will analyze patient and clinical factors that are associated with having a missing value. We will then perform analyses using multiple imputations to impute these key variables to allow analysis for all subjects and reduce any bias associated with the missing data. We will perform a sensitivity analysis to determine if missing values have an effect on study outcomes.

Baseline Analysis and descriptive statistics

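### A missing exit SBP is scored as the day's lowest chart reading while measured SBP is a mean of three, and the SAP states the substitution rule in ways that conflict

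*SAP*

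**What the plan says.** **Measured values.** SAP section 5 says of baseline and exit: "The average of the 3 blood pressure measurements is used". The protocol agrees. Under Enrollment and exit visits, "three BP consecutive measures are obtained and then averaged per NHANES protocol"; under Primary and secondary outcomes, "the study staff will ask the participant to measure blood pressure three times" and "The mean value for these readings will be used for the baseline and exit measurements, respectively".

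**Substituted values, SAP section 5.** "If participant failed to schedule an exit visit, blood pressures were extracted from the medical record for a 3-month period around the date"; the exit visit supplies that date. On which reading to take: "The lowest value will be used from the CDW for that day".

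**Substituted values, SAP section 6, Missing data analyses.** "If outcome is missing (e.g. exit blood pressure) then will use value in CPRS on the date closest to the exit date", with the limit "must be +/- 3 months around the date of the exit visit". This passage adds that outpatient pressures are to follow an EPRP definition held outside the SAP. It does not mention the lowest value.

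**Other relevant text.** The intention-to-treat sentence that opens SAP section 6 allows follow-up data up to the last available measurement before dropout. The Missing data analyses passage calls for multiple imputation once 15% or more of a key variable is missing, and promises an unspecified sensitivity analysis for missing values. Protocol section 5.6 (Study power and sample size) plans for 15% loss.

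**The concern.** A substituted participant's change score is a minimum minus a mean, whereas everyone else's is a mean minus a mean. The SAP gives no reason. On a day with several readings the minimum lies below the day's mean by construction, so the rule lowers the recorded exit pressure of exactly those participants who did not attend. Per participant, the gap can be about as large as the 4 mmHg in the primary hypothesis or the 5 mmHg used for power.

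The rule is also not stated consistently. Two programmers following sections 5 and 6 could pick different days, or different readings on the same day, for the same participant's primary outcome. And since the counting point for the 15% threshold is open, the SAP does not settle whether multiple imputation is run.

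**Working it through.** **1. Gap between the lowest reading and the day's mean.** The plan gives no figure for this. Take *k* readings on one day, independent and normal around the day's level with SD *s*. The expected gap is *c(k)* × *s*, with *c*(1) = 0, *c*(2) = 1/√π = 0.564 and *c*(3) = 1.5/√π = 0.846. The documents give neither *k* nor *s*; I assume *s* = 5 to 8 mmHg.

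| Readings that day | s = 5 | s = 8 |
|---|---|---|
| 1 | 0 | 0 |
| 2 | 2.82 | 4.51 |
| 3 | 4.23 | 6.77 |

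**2. Share that could be substituted.** Protocol section 5.6 supports three values:
- the stated loss, 15%;
- its count of 53 against 400 randomized, 53/400 = 13.25% (53 is in fact 15% of 354: 0.15 × 354 = 53.1);
- its reduction from 200 to 177 per arm, 23/200 = 11.5%.

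**3. Ceiling on the arm mean.** Suppose every lost participant had a chart day with two or three readings. Shift = share × gap.
- 11.5%: 0.115 × (2.82 to 6.77) = 0.32 to 0.78 mmHg
- 13.25%: 0.1325 × (2.82 to 6.77) = 0.37 to 0.90 mmHg
- 15%: 0.15 × (2.82 to 6.77) = 0.42 to 1.02 mmHg

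**4. Treatment contrast.** Let *f* be the substituted share and *g* the mean gap in each arm. The rule moves the contrast by *f*(intervention) × *g*(intervention) − *f*(control) × *g*(control). This is zero when the arms match. With equal *g*, each percentage point of difference in *f* moves it by 0.01 × (2.82 to 6.77) = 0.03 to 0.07 mmHg, in favour of the arm with more substitutions.

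**5. BP-control endpoint.** The lowest reading never exceeds the mean, so anyone at or below 120 systolic by the mean is also there by the lowest, and some others join them. That fixes the direction for the systolic part only. The endpoint also requires diastolic pressure at or below 80.

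**6. The substitution rules side by side.**

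| | SAP section 5 | SAP section 6, Missing data analyses |
|---|---|---|
| Trigger | no exit visit scheduled | any missing outcome |
| Window, read literally | 3 months in total | 3 months each side, 6 in total |
| Day | not defined | closest to the exit date |
| Reading | lowest that day | not stated; EPRP definition |
| Anchor | exit-visit date | exit-visit date |

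A reading 2 to 3 months from the anchor qualifies under section 6 but not under a centred section 5 window (1.5 months each side). The last-available-measurement wording is a third rule.

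**7. The 15% threshold.** At the stated 15% loss, the trigger of 15% or more is met before chart substitution. Each successful substitution lowers the count, so it may not be met afterwards. At 11.5% or 13.25% it is not met either way.

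**8. Is the day's mean exact?** Suppose a second reading is taken only after a first of 140 or more, the underlying day level has SD 14.2 (the protocol's SD) and its mean is 135 to 145 (assumed). Among those with two readings, the mean lies 0.5-2.0 mmHg above the underlying level, the lowest lies 2.0-3.3 below it, and the gap between them is 2.8-4.6. Neither is exact.

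**The case against.** The strongest reply is that no harm to the primary test is shown. The rule is worded the same for both arms and has no effect on single-reading days, and the documents do not report readings per day. Even a 10-point imbalance in substituted share would move the contrast by only 0.3-0.7 mmHg, against a target of 4-5. All of that stands. A reader might infer that the treatment effect is biased; the documents do not support this. The trial is unblinded, and only intervention participants have pressures taken on coaching calls and passed to providers when elevated. That makes unequal chart data possible but is not evidence of it. The net direction of a chart value against a study reading is also unknown, because setting and device differ.

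Other replies also stand in whole or part:
- **Anchor.** A reader might infer that no anchor date exists. SAP section 5 equates exit with 12 months, and the protocol speaks of a final 12-month exit call, so the due date is probably meant. The wording still points to a visit that was never scheduled.
- **Window.** Section 6 takes the closest date, so window length matters only when nothing nearer is available. The section 5 phrase may loosely mean three months each side.
- **BP control.** A reader might attach a size to the gain. None is established: diastolic pressure also limits control, and if repeats follow only high first readings, few would fall to 120.
- **Sensitivity analysis.** One is already promised. What is missing is its content.
- **EPRP.** That definition is not in the documents and may itself fix which reading is used.

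None of this removes the mixture of a minimum and a mean, or reconciles the two sections.

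**Conclusion.** The concern holds as a fault of definition and consistency, and should be fixed. Followed as written, section 5 scores substituted participants by a minimum and measured participants by a mean within one primary endpoint. On the assumed within-day SD, the cost is 2.8-6.8 mmHg per substituted participant with two or three readings that day and nothing with one; the arm-mean figures are ceilings. Bias in the treatment contrast is not shown, but without counts by arm a reader of the results could not rule it out. The 15% threshold is a live question at the protocol's stated loss, because the counting point decides whether multiple imputation is run. My confidence is medium, since readings per day, within-day variation and the EPRP definition are all unknown.

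**What to change.** - State one substitution rule and use it throughout SAP sections 5 and 6, including the last-available-measurement sentence. Give one trigger and one window by its total length, anchored on 12 months after randomization. The SAP's aims already use one year from randomization for administrative data.
- Use the mean of all eligible outpatient readings on the closest eligible date. If the EPRP definition fixes the lowest reading, or the primary rule is kept because data have already been extracted, keep the lowest, say why, and report the day's-mean version as a sensitivity analysis.
- Say whether the 15% threshold is counted before or after chart substitution.
- Specify the promised missing-data sensitivity analysis as one that excludes chart-substituted values.
- Report by arm the number substituted and the readings per substituted day.

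**Cost.** A dated SAP revision and some extra analysis. A repeat data pull is needed only if the window or anchor changes: section 5 describes several pressures as already extracted, with selection of the lowest still to come. No sample-size figure changes. Differences in setting and device remain, and the day's mean may run slightly high if repeats follow only high first readings.
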